#### Health economic evaluation

The resources needed to design and develop the DVD intervention will be recorded during phase 1. During the trial we will also record all resources required to provide the interventions in the DVD and the 'face-to-face' physiotherapy groups. Information will also be collected on all asthma-related healthcare costs for the 1-year follow up period. These will be collected using medical records to collect all asthma related NHS service use (primary and secondary care patient contacts, investigations and prescriptions) with maximum possible use of electronic records, supplemented where necessary by paper records. Respondent questionnaires will be completed at 3 month and 12 month data collection points to quantify time off work/college; and out of pocket expenses. This will constitute a societal perspective to the analysis.

Resources will be costed using appropriate local and national cost data. Total NHS and societal costs will be estimated for each group allowing estimates of the incremental costs of the breathing DVD and 'face-to-face' physiotherapy programmes compared to usual care. Health related quality of life will be assessed using the EuroQol (EQ5D) collected at baseline, 3, 6, and 12- months. These EQ5D scores will be used to generate quality adjusted life years (QALYs). No mortality differences are expected. The superiority analyses will include a cost-utility study (cost per QALY) and cost-effectiveness (cost per significant change in asthma-related health status, i.e. a change of 0.5 in the AQLQ score). If non-inferiority is proven between the face-to-face and DVD interventions, cost minimisation will be carried out. Where appropriate, incremental costeffectiveness ratios (ICERs) and cost-effectiveness acceptability curves (CEACs) will be estimated. Sensitivity analysis will be used to test any major assumptions made in the costing/analysis process. We will check for the extent of missing data at the analysis stage. If considered necessary, we will use appropriate statistical methods (for example multiple imputation) to impute missing data. This will be presented as a sensitivity analysis, i.e. in addition to the complete case analysis.

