#### Summary:

We aim to analyse 210 in each of the DVD and usual care arms and 105 in the face-to-face breathing retraining arm). Assuming a 10% dropout rate, we will therefore aim to recruit a total sample size of 585 patients (234 in each of the DVD and 'usual care' arms and 117 in the 'face-to-face' physiotherapy arm).

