#### Statistical Analysis:

#### 1. Analysis plan for equivalence study

Analysis and reporting of the equivalence comparison will follow published guidelines. It is known that full analysis set or ITT may lead to bias (from protocol violators, withdrawals and dropouts) and a resultant increase in type 1 error risk. Therefore, for the equivalence study, an ITT and a per protocol analysis will run simultaneously, neither having supremacy over the other. They should hopefully lead to similar conclusions giving the study a robust interpretation.

A 95% CI will be constructed for the mean difference in 12 month total AQLQ score between the DVD arm and the 'face-to-face' breathing retraining arm. Since the equivalence boundary is set at 0.3, equivalence will be declared if the 95% CI is wholly included between -0.3 and +0.3. If equality is not evident, then ANCOVA will be used to examine whether the 'face-to-face' breathing retraining arm is superior to the DVD arm via examination of the difference (and 95% confidence interval) of 12 month total AQLQ score (and each of the four domain scores) before and after adjustment for baseline AQLQ score and potential covariates such as age, gender, practice, smoking status etc.

BREATHE Page 27 of 35 Protocol v6 01-08-2014

ANCOVA will also be used to analyse the difference (and 95% confidence interval) for the secondary outcome measures (ACQ, lung function, fraction of exhaled nitric oxide, EuroQOL, anxiety and depression score, hyperventilation and patient enablement scores) at 12 months before and after adjustment for baseline values and potential confounders. Since we have data on AQLQ, ACQ and HADS at four time points (baseline, 3, 6 and 12 months) a repeated measures analysis will be used to examine change in each of these outcomes over time. For those secondary outcomes which involve count data (i.e. oral corticosteroid courses, bronchodilator use, asthma related healthcare resource use), Poisson regression analyses with a log link function will be performed to give rate ratios (and their 95% confidence intervals) in the DVD and 'face-to-face' breathing retraining arm both before and after adjustment for potential confounders such as smoking status and sociodemographic factors.

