#### 2. Analysis plan for superiority study

Baseline comparability between the three arms of the trial will be evaluated by examination of summary statistics (the mean and standard deviation or median and interquartile range for continuous variables, dependent on their distribution, and the number and percentage for categorical variables). In accordance with CONSORT guidelines, all comparative analysis will be conducted on an intention to treat (ITT) basis with a per protocol analysis performed as a sensitivity analysis.

For the primary outcome, analysis of covariance (ANCOVA) will be used to examine the 12-month total AQLQ score (and each of the four domain scores) across the three arms with initial adjustment for baseline AQLQ score and then for other potential covariates such as age, gender, practice, smoking status etc. Pair wise comparisons of AQLQ differences will be examined between the 'usual care' arm and each of the DVD and 'face-to-face' breathing retraining arms via calculation of one sided 95% confidence intervals. If the confidence interval includes +0.3 then superiority of either the DVD or 'face-to-face' breathing retraining arms over usual care will be rejected.

In a similar way, ANCOVA will also be used to analyse the continuous secondary outcome measures (ACQ, lung function, fraction of exhaled nitric oxide, EuroQOL, anxiety and depression score, hyperventilation and patient enablement scores). Since we have data on AQLQ, ACQ and HADS at four time points (baseline, 3, 6 and 12 months) a repeated measures analysis will be used to examine change in each of these outcomes over time. The 'usual care' arm will be compared to each of the DVD and 'face-to-face' breathing retraining arms in turn.

For those secondary outcomes which involve count data (i.e. oral corticosteroid courses, bronchodilator use, asthma related healthcare resource use), Poisson regression analyses with a log link function will be performed to give rate ratios in the DVD and 'face-to-face' breathing retraining arm compared to 'usual care' both before and after adjustment for potential confounders such as smoking status and sociodemographic factors.

BREATHE Page 28 of 35 Protocol v6 01-08-2014

Data and all appropriate documentation will be stored for a minimum of 5 years after the completion of the trial, including the follow-up period.

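### Three secondary count outcomes are assigned Poisson regression with no provision for overdispersion; if the variance is 1.5 to 3 times the mean, nominal 5% tests run at about 11% to 26%

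*Protocol*

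**What the plan says.** Protocol section 8.1 has two analysis plans, and both name a model for the count outcomes.

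- **Superiority plan (each intervention against usual care).** The outcomes are listed: "For those secondary outcomes which involve count data (i.e. oral corticosteroid courses, bronchodilator use, asthma related healthcare resource use". The method is then given: "Poisson regression analyses with a log link function will be performed to give rate ratios in the DVD" and face-to-face arms relative to usual care. The models are to be run "both before and after adjustment for potential confounders such as smoking status and sociodemographic factors".
- **Equivalence plan (DVD against face-to-face).** The same outcomes get the same model: "Poisson regression analyses with a log link function will be performed to give rate ratios (and their 95% confidence intervals) in the DVD" and face-to-face arms. Only this sentence promises 95% confidence intervals for the counts; the superiority sentence promises rate ratios alone.

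The text gives the model family, the link and the effect measure. It does not give the variance estimator. Nowhere does the protocol mention overdispersion, a scale parameter, robust standard errors, negative binomial regression or a check of the variance assumption. It gives no expected rate or variance for any of the three outcomes.

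**The concern.** A Poisson model sets the variance equal to the mean. That holds for per-patient counts when all patients with the same covariates share one underlying rate. If their rates differ, the variance exceeds the mean, and the default model-based standard errors are too small.

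Several features of the protocol make unequal rates likely:

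- Entry is deliberately broad, with smokers included and no requirement to demonstrate reversibility (sections 4.2 and 4.3).
- The background (section 1.1) describes asthma as covering several phenotypes.
- Patients come from about 20 practices (section 4.1).
- The covariates named as examples for the count models are smoking status and sociodemographic factors. Baseline exacerbation frequency is collected (section 4.1) but not named there. Practice is named for the AQLQ analysis but not for the counts.

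The unit of bronchodilator use is also not stated in section 8.1. Recording the same use in units c times smaller multiplies the mean by c and the variance by c², so the variance/mean ratio rises by a factor of c. Model-based Poisson standard errors therefore depend on an arbitrary choice of unit; robust or scaled ones do not.

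At stake are the trial's statements on steroid courses, reliever use and service use. These are secondary endpoints, but asthma-related health resource use is named in the second trial objective, which the synopsis lists among the primary objectives.

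**Working it through.** **Inputs from the protocol**

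- Analysed numbers: "We aim to analyse 210 in each of the DVD and usual care arms and 105 in the face-to-face breathing retraining arm" (section 8.1, Summary).
- Attrition: "Assuming a 10% dropout rate" (same place).
- Observation period: "Information will also be collected on all asthma-related healthcare costs for the 1-year follow up period" (section 7, Health economic evaluation).
- Rates, variances, power or sample size for the count outcomes: none given. There is therefore no stated figure on this point to reproduce.

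The arm sizes themselves reproduce: 210/0.9 = 233.3, rounded up to 234, and 105/0.9 = 116.7, rounded up to 117, as the protocol has them.

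**Assumption**

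Let φ be the variance/mean ratio after covariates. The protocol does not give φ, so a range is used.

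**Step 1. Where φ comes from.** If each patient has their own Poisson rate, and the rates vary between patients with coefficient of variation CV, then

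φ = 1 + mean × CV².

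Two assumed examples:

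- mean 0.5 and CV 1 give φ = 1 + 0.5 × 1 = 1.5;
- mean 3 and CV 0.5 give φ = 1 + 3 × 0.25 = 1.75.

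**Step 2. Effect on error rate and coverage.** The true standard error is √φ times the model-based one. So

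- actual two-sided error = 2 × [1 − Φ(1.96/√φ)];
- actual coverage of a nominal 95% interval = 1 minus that error;
- planned interval width as a fraction of the correct width = 1/√φ.

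| φ (assumed) | √φ | 1.96/√φ | Actual error | Coverage | Width fraction |
|---|---|---|---|---|---|
| 1 | 1.00 | 1.96 | 5.0% | 95% | 1.00 |
| 1.5 | 1.22 | 1.60 | 11.0% | 89% | 0.82 |
| 2 | 1.41 | 1.39 | 16.6% | 83% | 0.71 |
| 3 | 1.73 | 1.13 | 25.8% | 74% | 0.58 |

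**Step 3. Check by simulation.** Counts were drawn with a true rate ratio of 1 (10,000 runs per scenario), from a Poisson distribution for φ = 1 and a negative binomial otherwise. They were analysed without covariates by the model-based Poisson Wald test at the protocol's arm sizes. Means and φ are assumptions.

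| Mean | φ | Error, 210 v 210 | Error, 105 v 210 |
|---|---|---|---|
| 0.5 | 1 | 5.3% | 5.0% |
| 0.3 | 1.3 | 8.6% | 8.1% |
| 0.5 | 1.5 | 11.0% | 10.8% |
| 0.5 | 2 | 15.9% | 16.1% |
| 3 | 2.5 | 21.1% | 21.2% |

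The simulated rates agree with the formula where the same φ was used, and they hardly depend on arm size or allocation ratio. With robust or Pearson-scaled variance on the same data, the error rate was between 4.7% and 5.7% in every scenario, including φ = 1. A fitted negative binomial model was not simulated.

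**The case against.** The strongest reply is that the protocol does not prescribe a faulty analysis. Poisson regression with a log link and robust or scaled standard errors fits its wording exactly, and the method for standard errors is a detail that a statistical analysis plan often supplies. That plan was not available. This stands in part. A reader might infer that the protocol ties the trial to default model-based standard errors; the text does not say so. It remains that the protocol chose a model, stated it twice, and attached no safeguard, so an analyst who follows it with default settings gets intervals that rely on the variance equalling the mean.

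A second reply is that harm is not shown. That also stands. No rate or variance is given, the population is described as mild to moderate, and the adjusted models may absorb some of the variation between patients. At φ = 1 nothing goes wrong. A reader might infer that false-positive rate ratios will follow; the documents support only that they become more likely if the counts are overdispersed, which is probable here but not demonstrated.

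A third reply is that little rests on these outcomes. They are secondary, no decision rule is attached to them, and the costing work in section 7 does not rely on these models. This limits the importance of the point but does not remove it, because the rate ratios will still be reported and interpreted.

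**Conclusion.** The concern holds in a conditional form. Both analysis plans assign Poisson regression to three secondary count outcomes with no provision for overdispersion. For an assumed variance/mean ratio between 1.5 and 3, nominal 5% two-sided tests would run at about 11% to 26%, and intervals would be 0.82 to 0.58 of their proper width. This rests on two conditions: that default model-based standard errors are used, which the text neither requires nor excludes, and that overdispersion of that size remains after covariates, which the protocol gives no data to confirm.

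It would be wrong to read this as a threat to the trial's main result. The AQLQ superiority and equivalence analyses do not use the count models and are unaffected.

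**What to change.** In both analysis plans of section 8.1, state that the count outcomes will be analysed by Poisson regression with robust (sandwich) or Pearson-scaled standard errors, or by negative binomial regression, with log follow-up time as offset. Either route is acceptable; putting negative binomial first would be a preference, not a requirement. The offset is a separate matter from overdispersion: it keeps the estimates interpretable as rate ratios when patients are observed for unequal times, as the assumed 10% dropout makes likely.

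The cost is one sentence in each plan and one model option, with no extra patients or data. Confidence intervals become somewhat wider if the counts are overdispersed, which is the correction intended. If they are not, the loss is almost nil: at φ = 1 the simulated error rate with robust or scaled variance stayed at about 5%.

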#### 4. SELECTION AND ENROLEMENT OF SUBJECTS

#### 4.1 SCREENING AND PRE-REGISTRATION / RANDOMISATION EVALUATIONS

We plan to recruit 585 patients (234 in each of the DVD and 'usual care' arms and 117 in the 'face-to-face' physiotherapy arm) from 20 general practice centres, aiming for up to 30 subjects per GP centre. All general practices now have 'asthma registers' of all patients with currently active asthma, as this is a requirement for payment under the NHS Quality and Outcomes Framework system. Patients on the practice asthma register meeting the inclusion criteria below and who have received prescriptions for any asthma medication in the previous 12 months will be identified from the practice computer records by practice staff. A mail merge will be performed at the practice sending out a study invitation letter with full information. People wishing to have more information about the trial will be provided with contact telephone numbers to enable them to speak to study staff at the University of Southampton Clinical Trials Unit (UoSCTU), or encouraged to talk to their GP. People potentially interested in study participation will be asked to provide contact details, to complete the mini-AQLQ (Asthma Quality of Life Questionnaire (23) and to

BREATHE Page 17 of 35 Protocol v6 01-08-2014

return these to the Study Co-ordinator in a pre-addressed stamped envelope. Only those with impaired health status (AQLQ score <5.5) will be recruited, as lack of impairment in health status does not allow 'room for improvement' in the primary outcome measure. In our previous work and other studies, 75% or more or people with asthma treated in the community have impaired health status.

Subjects meeting the entry criteria will be given an appointment to see the study nurse for the baseline visit, which will occur at the subject's general practice at a mutually convenient time. Any questions about the study will be answered, and informed consent obtained. A study nurse will perform the baseline assessment. This will consist of:

- Facilitating subject completion of validated questionnaires: Disease-specific health status (AQLQ) (23), Nijmegen hyperventilation questionnaire (24), Generic health status (EuroQOL, EQ-5D) (25); anxiety and depression scores (HAD questionnaire) (26), Asthma control questionnaire (ACQ) (27).
- Clinical details: Smoking status, asthma history, co-morbidities, medication, and exacerbation frequency.

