#### 4.2 INCLUSION CRITERIA

- Full practice registration for a minimum of 12 months prior to enrolment
- Age 16-70 yrs
- Physician diagnosed asthma in medical record
- ≥1 anti-asthma medication prescription in the previous year (determined from the physician prescribing records)
- Impaired asthma-related health status (Asthma Quality of Life Questionnaire score of <5.5)

- Informed consent

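### The adjusted count models name no pre-randomisation value, although exacerbation frequency and medication are recorded at baseline

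*Protocol*

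**What the plan says.** All references are to the Protocol.

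- **Count outcomes.** Section 8.1 treats three secondary outcomes as counts: "oral corticosteroid courses, bronchodilator use, asthma related healthcare resource use". For the superiority comparison, "Poisson regression analyses with a log link function will be performed to give rate ratios in the DVD and 'face-to-face' breathing retraining arm" relative to usual care, first unadjusted and then with "adjustment for potential confounders such as smoking status and sociodemographic factors". The equivalence plan uses the same covariate wording for DVD against face-to-face.
- **Continuous secondary outcomes.** The equivalence plan analyses these "at 12 months before and after adjustment for baseline values and potential confounders", so baseline values and confounders appear as two separate items. The superiority plan first adjusts the primary AQLQ analysis for baseline AQLQ and then says: "In a similar way, ANCOVA will also be used to analyse the continuous secondary outcome measures". Baseline adjustment is therefore implied.
- **Data available at baseline.** Section 4.1 lists "Clinical details: Smoking status, asthma history, co-morbidities, medication, and exacerbation frequency" among the baseline assessments. Section 4.2 requires "Full practice registration for a minimum of 12 months prior to enrolment".
- **Data window for resource use.** The health economic evaluation in section 7 describes collection for the follow-up year. The schedule of observations places the medical notes review at 12 months. Neither mentions a window before randomisation.

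**The concern.** A patient's own history is the obvious candidate predictor of later steroid courses or reliever use. The plan applies that principle to the continuous secondary outcomes and then, for the counts, gives only smoking and sociodemographic background as examples. The equivalence plan lists baseline values separately from confounders, so a reader would not naturally take the count wording, which keeps only confounders, to include a baseline count.

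If the models are fitted as described, the rate ratios vary more from sample to sample than they need to. They are also more exposed to a chance excess of exacerbation-prone patients in one arm. This matters most where the sample is smallest, in comparisons with the face-to-face arm (105 to be analysed). The counts are secondary endpoints, but asthma-related resource use also appears in the second trial objective.

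**Working it through.** **1. Is there a figure in the plan to reproduce?** No. The protocol states no rate, variance or power for any count outcome. The arm sizes used below do agree with the plan: 210/0.9 = 233.3, rounded up to 234; 105/0.9 = 116.7, rounded up to 117; 234 + 234 + 117 = 585.

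**2. The text side by side.**

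| Outcome | Equivalence plan | Superiority plan |
|---|---|---|
| Primary AQLQ | CI for the 12-month mean difference, no baseline adjustment named; ANCOVA with baseline only if equivalence is not shown | Adjusted for baseline AQLQ |
| Continuous secondaries | Before and after adjustment for baseline and confounders | By reference to the AQLQ model |
| Counts | Before and after adjustment for confounders (open list) | Same wording |

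**3. What the baseline data cover.** Exacerbation frequency is a proxy for steroid courses and, more loosely, for resource use. Medication covers bronchodilators, but the protocol does not say that use is quantified. No baseline resource-use count is described.

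**4. Size of the gain from a like-for-like prior count.** All inputs except the arm sizes are assumptions.

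- Arms 210 v 210, no treatment effect, 600 runs per scenario.
- Patient rate = mean × exp(s·u − s²/2), with u standard normal and s² = log(1 + V). V, the between-patient variance relative to the mean squared, is 0.5, 1 or 2.
- The two years' log rates are correlated 0.5 or 0.8. Counts are Poisson given the rate.
- Poisson log-link fit with and without log(prior count + 0.5).
- Variance cut = 1 − (SD adjusted / SD unadjusted)². SD is the run-to-run spread of the log rate ratio. The spread is used because the model-based Poisson standard error ignores variation between patients.

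| Mean per year | Variance ratio | Variance cut |
|---|---|---|
| 0.3 | 0.97-1.00 | 0-3% |
| 0.5 | 0.91-1.00 | 0-9% |
| 1 | 0.76-1.00 | 0-24% |
| 6 | 0.60-0.91 | 9-40% |

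Worked upper ends (V = 2, correlation 0.8):

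- At 6 per year: 1 − (0.110/0.142)² = 1 − 0.600 = 40%.
- At 1 per year: 1 − (0.145/0.166)² = 1 − 0.763 = 24%.

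On the standard-error scale the largest gains are 1 − √0.91 = 5% at 0.5 per year, 1 − √0.76 = 13% at 1 per year and 1 − √0.60 = 23% at 6 per year.

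**5. Bias.** The mean log rate ratio stayed within 0.013 of zero with and without the covariate, as expected under randomisation.

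**6. Best case.** If each patient has exactly the same underlying rate in both years (gamma-distributed, shape 0.5 to 2, covariate log(prior count + 1), 400 runs per cell), the cuts are 4-24% at 0.5 per year, 11-38% at 1, 37-78% at 4 and 63-89% at 8. In the same model at 105 v 210 the proportional gain is similar, but the standard error starts higher: 0.139 against 0.104 at 4 per year, shape 1.

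**The case against.** The strongest reply is that nothing is excluded. The covariate list is given by example, and the final covariate set for secondary models is commonly settled in the analysis plan, which is not shown. Section 3.1 also frames the outcome measures, counts included, as changes from baseline to 12 months. This stands as far as it goes: a baseline value is unnamed, not ruled out. But section 3.1 sets no regression covariate, and the examples chosen leave out the one kind of variable that the same section names for the continuous secondaries.

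A reader might infer more than the documents support in four ways:

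- **That the counts are treated unlike every continuous outcome.** They are not. The confidence interval that decides equivalence on AQLQ names no baseline adjustment. The continuous secondaries in the equivalence plan are also reported unadjusted. Patient enablement is among the ANCOVA outcomes but appears in no baseline assessment.
- **That the rate ratios are biased.** Randomisation prevents this; only precision and chance imbalance are at stake.
- **That large gains, up to 89%, are on offer.** Those need perfectly stable patient rates and a like-for-like prior-year count that the plan does not collect.
- **That prior-year counts are already in hand because of the 12-month registration rule.** The rule suggests that a record should exist. It does not show that counts are extracted from it.

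**Conclusion.** The point holds as a modest, inexpensive improvement to secondary analyses. Neither plan names a pre-randomisation value for any of the three counts, while relevant baseline data are recorded anyway.

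For rare events such as steroid courses at 0.3-0.5 per year, the expected gain is small and may be nil (0-9% of the variance). At 1 per year it is 0-24%, and for frequent counts at 6 per year 9-40%. These figures assume the event rates, the spread between patients and a between-year correlation of 0.5-0.8 in log rates; the protocol supplies none of them. They describe a like-for-like prior count. No gain has been calculated for exacerbation frequency or baseline medication used as proxies, and it may be smaller. The primary outcome is unaffected.

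**What to change.** In both analysis plans in section 8.1, name the following in the adjusted Poisson models, alongside the covariates already given:

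- baseline exacerbation frequency, for oral steroid courses and for asthma-related resource use;
- baseline bronchodilator medication, in whatever detail the baseline form records it, for bronchodilator use.

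The unadjusted rate ratios can stay as planned. The cost is wording only, because the data are already collected at the baseline visit.

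Optionally, extend the 12-month notes review to the 12 months before randomisation, so that each count has a prior value from the same source. This needs no extra visit or patient contact, but it adds extraction for up to 585 records. It is better decided before the notes reviews begin, and weighed against the small gain expected for rare events.
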